13. MEDICATIONS

Medications defined as concomitant medications (as identified below) will be presented for the SAF and coded using the World Health Organization (WHO) dictionary. The version will be established and documented prior to lock of the data and will be identified within footnotes. Medications will be classified and summarized by anatomical therapeutic chemical (ATC) drug class and by the WHO drug preferred name. Subjects who report use of more than one medication or multiple uses of the same medication will be counted once per medication code and once for all drugs taken within an ATC drug class.

Concomitant medications will also be summarized based on the number of subjects with changes to AD medication between the first and last dose of OLE treatment. The number of subjects will be presented along with the incidence of AD medications by WHO drug preferred name.

If the medication start date is missing or partial, the date will be compared as far as possible with the date of first dose of the OLE study drug. Medications will be assumed to be concomitant unless there is clear evidence (through comparison of partial dates and/or collected assessment of whether the medication started prior to the first dose of the study drug) suggesting the medication started prior to the first dose of study medication.

[REDACTED] [REDACTED]

Author: [REDACTED]

Version Number:

7

Version Date:

07Dec2023

Template No.: CS_TP_BS016 Revision 6

Reference: CS_WI_BS005

Effective Date: 02Dec2019

- ‘Prior’ medications are medications which have a start date prior to the first dose of OLE study drug and will include those medications which were identified as ongoing at the end of double-blind and re-entered onto an Ongoing Concomitant Medication page of the OLE eCRF form.
- ‘Concomitant’ medications are all medications which have a start date on or after the date of the first dose of OLE study drug.

All medications captured in the OLE eCRF concomitant medications form will be listed, ordered within subject by the medication start date. The listing will display the recorded term from the CRF and, adjacent to that, the preferred name that appears in the tables.

14. SUBSTANCE USAGE

Substance usage history was not re-assessed after double-blind baseline and will not be included in any OLE listings.

15. STUDY MEDICATION EXPOSURE

Duration of treatment in the OLE will be summarized as both total days and total weeks per subject and will be presented using the descriptive statistics including mean (SD), 25th percentile, median, 75th percentile, min and max for the SAF. Similarly, duration of total gantenerumab exposure spanning the double-blind and OLE periods, duration of gantenerumab exposure at the highest dose in the OLE and duration of gantenerumab exposure at the highest dose in either the double-blind or OLE period will be summarized.

The total number of administered doses (including both fully and partially administered) for each subject will be summarized overall and by dose levels using descriptive statistics. The cumulative OLE dose exposure will be summarized. A listing of OLE study drug administration

Author: [REDACTED]

Version Number:

7

Version Date:

07Dec2023

Template No.: CS_TP_BS016 Revision 6

Reference: CS_WI_BS005

Effective Date: 02Dec2019

will be presented. In addition, percent compliance will be summarized during the OLE.

Study medication exposure will be summarized for the interim analysis.

15.1. DERIVATIONS

Duration of treatment from OLE baseline (days) = date of last OLE dose – date of first OLE dose
+1

Total duration of treatment with gantenerumab from double-blind baseline (days) = (date of last double-blind dose – date of first double-blind dose) + (date of last OLE dose – date of first OLE dose) +1

Duration of treatment of gantenerumab at the highest OLE dose received (days) = date of last OLE dose – date of first OLE dose at the same dose level +1

Duration of treatment of gantenerumab at the highest dose received (days) = date of last dose at the highest level in either the OLE or double-blind periods – date of first dose at the same dose level +1

Percent compliance in the OLE = (number of OLE doses/ number of planned OLE dosing visits prior to treatment discontinuation) x 100, where the number of OLE doses combines dosing at the visit and the preceding Q2W dosing timepoint, where applicable, as a single dose

Cumulative OLE dose of gantenerumab = sum of all OLE doses, based upon the planned dose for any dose administered.

Author: [REDACTED]

Version Number:

7

Version Date:

07Dec2023

Template No : CS_TP_BS016 Revision 6

Reference: CS WI BS005

Effective Date: 02Dec2019

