3.3 Number of Participants and Sites

Individuals will be recruited by host DIAN-TU sites and may also come from other sources such as referring partner sites, and the DIAN-EXR. DIAN-TU sites are located globally. The number of sites and locations may be expanded over the course of the study.

Recruitment of mutation positive participants is with baseline CDR 0 to 1 (inclusive). Mutation positive groups (active vs. placebo) will be enrolled to meet the respective enrollment numbers of asymptomatic (CDR 0) and symptomatic (CDR > 0) participants.

For the gantenerumab and solanezumab arms, a total of 193 participants were enrolled into the double-blind period (144 mutation carriers and 49 mutation non-carriers) with 52 mutation carriers on active gantenerumab, 52 mutation carriers on active solanezumab, and 40 mutation carriers in the pooled placebo arm.

The CRI period may recruit up to 740 participants during any time where a drug arm is not actively randomizing to meet the enrollment required for the three tau-targeted drug arms slated for secondary prevention enrollment (Tau NexGen) and the drug arm(s) slated for primary prevention. Up to 500 participants between 10 years younger than their estimated years to symptom onset (EYO) and 10 years after estimated symptom onset (-10 and + 10 EYO) may be

enrolled in the CRI period if no study drug arm is available for immediate enrollment into DIAN-TU-001, or if a future study drug arm is stopped prior to the planned completion (e.g., at biomarker interim, drug toxicity), to ensure that a sufficient number of active and eligible participants qualify for entry into a drug arm once opened for randomization. In addition, up to 240 participants may be enrolled in the CRI period to establish a trial-ready cohort of participants who are 11 to 25 years younger than their estimated symptom onset (EYO –25 to –11) and are at least 18 years old and cognitively normal (CDR 0) (primary prevention population).

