1.9.2 Open-Label Extension

Primary endpoints for the OLE include cerebral amyloid imaging using [¹¹C]PiB-PET as well as the safety and tolerability of treatment with gantenerumab at higher doses.

Additional study endpoints for the gantenerumab OLE will be specified in the gantenerumab-specific SAP. The objectives of the OLE are as follows:

- (i) To enable participants, who have committed as much as 4 to 7 years to the double-blind treatment period of the study, to continue or begin to receive gantenerumab, which improves critical markers of their progressive disease, following their participation in the longest placebo-controlled trial in DIAD;
- (ii) To determine if continued treatment with gantenerumab at its target dose can result in complete removal of brain amyloid;
- (iii) To investigate which non-amyloid related downstream biological measures (e.g. tau and markers of neurodegeneration) can be improved or normalized with complete removal of amyloid at different stages of disease;
- (iv) To investigate the relationship of these biological measures with cognitive and clinical findings; and
- (v) To assess the summation of gantenerumab's effect on biomarkers during the entire double-blind period and open label extension period, including the common close portion in which biomarkers were not assessed (i.e., from year 4 to 7).

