The double-blind period had two arms for each study drug, the active study drug and the blinded placebo for that study drug. Subjects were recruited from various sources, i.e., participating DIAN-observational (DIAN-OBS) study sites, DIAN-TU-001 trial sites, DIAN-TU-001 partner sites, the DIAN Expanded Registry study, and families identified by the sites. Mutation positive subjects who signed the informed consent form (ICF), met eligibility requirements and completed all baseline evaluations were randomized in a 3:1 ratio to receive either the active study drug or placebo for the active study drug. Eligible subjects were offered the opportunity to receive active drug for up to 3 years in an open label extension.

Mutation positive subjects who were administered either gantenerumab/placebo to gantenerumab or solanezumab/placebo to solanezumab were allowed to participate in the OLE for gantenerumab. All subjects participating in the OLE will receive gantenerumab. Dosing and titration for the OLE can be found in Section 1.5.2 of Appendix 3 of the protocol.

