5.5. SAFETY ANALYSIS SET [SAF]

The safety analysis population includes all subjects who have consented to participate and have received at least one dose of study drug in the gantenerumab OLE period.

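### SAP 15.1's formula for total gantenerumab duration has no condition on double-blind arm, so read literally it counts placebo and solanezumab time as gantenerumab exposure

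*SAP*

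**What the plan says.** SAP Section 15 plans a descriptive summary, for the safety set, of "duration of total gantenerumab exposure spanning the double-blind and OLE periods". Section 15.1 names the variable and starts its definition: "Total duration of treatment with gantenerumab from double-blind baseline (days) = (date of last double-blind dose". In full, the calculation is "date of last double-blind dose – date of first double-blind dose) + (date of last OLE dose – date of first OLE dose) +1". The double-blind term refers to double-blind doses of any kind, and neither section limits it to one arm.

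The safety set (SAP Section 5.5) is everyone who consented and who "have received at least one dose of study drug in the gantenerumab OLE period". SAP Section 3.1 says that mutation-positive subjects who "were administered either gantenerumab/placebo to gantenerumab or solanezumab/placebo to solanezumab were allowed to participate in the OLE for gantenerumab", and that "All subjects participating in the OLE will receive gantenerumab". The safety set can therefore hold people from all double-blind groups. SAP Section 5 and SAP Appendix 1 set the general table columns as Placebo, Solanezumab, Gantenerumab and Total. Section 15 also schedules the exposure summary for the interim analysis.

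**The concern.** For someone who took placebo or solanezumab in the double-blind period, the first term of the formula measures time on a different treatment. The label promises time on gantenerumab, but the arithmetic gives time on any blinded study drug plus time on open-label gantenerumab.

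A programmer who follows the SAP as written would produce an exposure table in which former placebo and solanezumab participants show years of gantenerumab that they never received. Any pooled column would carry the same error. Cumulative exposure is one of the first tables that a reader of a study report uses to judge how much experience lies behind the safety findings.

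**Working it through.** The documents state no figure for this variable, so there is none to reproduce. The check applies the formula literally and then with the double-blind term limited to the gantenerumab arm.

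**Inputs**
- Double-blind length: 208 to 364 weeks (Protocol Sections 6.3.4 and 6.3.5). Protocol Appendix 3, Section 1.9.2 agrees, describing participants "who have committed as much as 4 to 7 years to the double-blind treatment period of the study".
- OLE length: up to 156 weeks (Protocol Appendix 3, Section 2.2). No drug is given at OLE V40 (Section 3.2.5 there), so the last scheduled dose is at week 154. A 104-week span is used as a shorter example.
- Double-blind carriers: "52 mutation carriers on active gantenerumab, 52 mutation carriers on active solanezumab, and 40 mutation carriers in the pooled placebo arm" (Protocol Section 3.3), 144 in all.

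**Formulas, in days**
- Literal: 7 × DB weeks + 7 × OLE weeks + 1.
- Correct for a former placebo or solanezumab participant: 7 × OLE weeks + 1.
- Excess: 7 × DB weeks, the whole double-blind span.

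**Results for a former placebo or solanezumab participant**

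| DB weeks | OLE weeks | Literal | Correct | Excess | Ratio |
|---|---|---|---|---|---|
| 208 | 154 | 1,456 + 1,078 + 1 = 2,535 | 1,079 | 1,456 | 2.35 |
| 364 | 154 | 2,548 + 1,078 + 1 = 3,627 | 1,079 | 2,548 | 3.36 |
| 208 | 104 | 1,456 + 728 + 1 = 2,185 | 729 | 1,456 | 3.00 |
| 364 | 104 | 2,548 + 728 + 1 = 3,277 | 729 | 2,548 | 4.50 |

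The excess is 3.99 to 6.98 years. With a 156-week span and the +1 ignored, the ratios are (208 + 156)/156 = 2.33 and (364 + 156)/156 = 3.33. Values for the gantenerumab arm do not change.

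**How many people could be affected**
- Double-blind carriers not on gantenerumab: 52 + 40 = 92, and 92/144 = 64%.
- The OLE arm mix is not given. Protocol Appendix 3, Section 4.1.2 aims for 60 to 90 of the 144. If that goal was met, at least 60 − 52 = 8 to 90 − 52 = 38 participants came from other arms, even if every gantenerumab participant enrolled.

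**Total column, assuming the OLE kept the 52:92 mix**
- Shortest double-blind, 154-week OLE: correct mean = (52 × 2,535 + 92 × 1,079)/144 = 1,605, and 2,535/1,605 = 1.58.
- Longest double-blind, 104-week OLE: correct mean = (52 × 3,277 + 92 × 729)/144 = 1,649, and 3,277/1,649 = 1.99.

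Under that assumption the pooled mean is overstated about 1.6 to 2.0 times.

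**Does another section supply the missing condition?** None does for this formula. The SAP draws the distinction elsewhere. Section 10 limits double-blind baseline values to those randomized to gantenerumab. Section 5.3 anchors the All Gant exposure population on the first gantenerumab period. Section 18.7.2 takes the antibody baseline before first gantenerumab exposure in either period.

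**The case against.** The strongest reply is that the label supplies the restriction. Only the double-blind gantenerumab arm has gantenerumab treatment counted from double-blind baseline, and the neighboring derivation from OLE baseline already gives the right figure for everyone else. The SAP separates the arms elsewhere, so a careful programmer would probably do so here. The column layout is a general convention; SAP Section 8 leaves table content to templates that are not in the documents, so it cannot be confirmed that this row is filled for the placebo and solanezumab columns. More than four years of gantenerumab in a placebo column, beside an OLE of at most three, would also be noticed.

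Much of this stands as evidence of intent, and it is why the matter is small. It does not change the formula. If the variable were meant only for the gantenerumab arm, the SAP would have no derivation of total exposure for the rest of the safety set, although Section 15 plans the summary for that set. A clarifying sentence is needed on either reading.

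A reader might also infer that safety rates or the interim conclusion depend on this variable. The documents do not support that. SAP Section 18 plans counts and percentages, overall, by dose level and by visit, with no exposure-adjusted rates. The interim objective in SAP Section 4.3 mentions long-term treatment, but the interim primary analyses in Section 17 are Cox models that do not use this duration. The exposure model in Section 16.1.4.5 uses cumulative OLE dose.

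**Conclusion.** The point holds for the formula as written: without an arm condition, it reports non-gantenerumab time as gantenerumab exposure for any former placebo or solanezumab participant. The excess is that person's whole double-blind dosing span. On protocol durations this inflates the value about 2.3 to 3.4 times with a full OLE, and 3.0 to 4.5 times with a 104-week OLE.

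The ratios are illustrations. They assume that the double-blind dosing span equals the protocol period; 364 weeks is the protocol maximum, and someone who stopped blinded dosing early would have a smaller excess. The SAP's version history records that the OLE ended early, which shortens the OLE term and raises the ratio. It would be too strong to say that 64% of OLE participants are affected, or that a typical former placebo participant will be shown with 7 to 10 years: the first figure describes the double-blind arms and the second assumes a full OLE.

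The consequence is limited to one descriptive exposure summary at the interim and final analyses. The primary MMRM, the Cox models, the exposure model and the adverse-event summaries are unaffected. It is a minor correction, but a clear one.

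**What to change.** Restate the derivation in SAP Section 15.1 with a condition on arm:

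- Randomized to gantenerumab in the double-blind period: (last double-blind dose − first double-blind dose) + (last OLE dose − first OLE dose) + 1, as now.
- All others: last OLE dose − first OLE dose + 1.

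The cost is one condition in the SAP and in the program. If exposure tables already exist, check whether the program applied the condition and rerun the summary if it did not. No endpoint, model or analysis set changes.

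A separate, optional change is to count each period inclusively. Two dosing spans with a single +1 count one day too few, so +1 per period would add one day to each gantenerumab-arm value. If adopted, it should be stated as its own change, because it alters values that the arm condition leaves alone.

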16. EFFICACY OUTCOMES

16.1. PRIMARY EFFICACY

16.1.1. PRIMARY EFFICACY VARIABLE(S) & DERIVATION(S)

The primary efficacy variable is the change in amount of amyloid deposition as measured by [11C]PiB-PET. The composite PiB partial volume corrected standardized uptake value ratio (C-SUVR, the composite SUVR of precuneus, caudate, gyrus rectus, occipital cortex, parietal cortex, prefrontal cortex and temporal cortex) is used as the biomarker endpoint for amyloid deposition. Corresponding analyses based on conversion of SUVR to centiloid will be performed by Washington University.

16.1.2. MISSING DATA METHODS FOR PRIMARY EFFICACY VARIABLE(S)

There will be no missing data imputation for the primary efficacy variable.

16.1.3. PRIMARY ANALYSIS OF PRIMARY EFFICACY VARIABLE(S)

The primary objective for the OLE is to determine if treatment with gantenerumab at its target dose can result in removal of brain amyloid plaque using cerebral amyloid imaging using [11C]PiB-PET.

The primary efficacy analysis will be performed for the OLE Gant mITT without the use of controls in the model. A Mixed-Effects MMRM analysis will be used to test if the change from the OLE baseline to the end of OLE in PiB-PET SUVR is significantly less than 0 for the OLE Gant mITT population. The MMRM will include the OLE baseline PiB-PET SUVR and visit (treated as categorical) as the fixed effects. An unstructured variance-covariance matrix will be

Author: [REDACTED]

Version Number:

7

Version Date:

07Dec2023

Template No.: CS_TP_BS016 Revision 6

Reference: CS_WI_BS005

Effective Date: 02Dec2019

used to model the within-subject errors among the repeated measures. If the unstructured covariance structure matrix results in a lack of convergence, the following covariance structures will be assumed in sequence: heterogeneous Toeplitz, heterogeneous autoregressive, heterogeneous compound symmetry, and compound symmetry. The corresponding p-value and the 95% confidence interval for the estimated least squares mean change at each visit will be presented. If the upper bound of the 95% CI at the year 3 OLE visit is less than 0, it is concluded gantenerumab significantly removes amyloid plaque at year 3. In the case that a structured variance-covariance matrix is used to enable the model to converge, the "sandwich" estimator of the variance-covariance matrix will be employed by using the "empirical" option in the proc mixed procedure. P-values for within-subject change resulting from a one-sample t-test using least squares mean estimates and associated standard errors will be presented.

Descriptive statistics including number of observations, mean, SD, median, minimum, and maximum will be provided by visit. P-values for within-subject change resulting from a one-sample t-test using least squares mean estimates and associated standard errors will be presented. In addition, a listing of the primary endpoint will be presented.

Figures of model estimated mean over time or spaghetti plots of individual data over time/EYO color-coded by treatment arms and doses will be presented as deemed necessary by Washington University team and may be included in CSR as needed.

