1.5.2.2 PK/PD (Amyloid PET) Model-Based Dose Selection

Comparison of PET data from DIAD and sporadic AD (sAD) studies indicated that DIAD participants with mutations have higher amyloid growth rates and lower amyloid plaque removal following administration of gantenerumab than participants in sAD studies who received a similar gantenerumab regimen. Extensive analyses were performed of the double-blind period data and a combined sAD–DIAD PK/PET model of gantenerumab was developed to assess the effect of gantenerumab on amyloid plaque removal (PK/PD Model). The quantitative results suggest that an approximate 3-fold higher dose of gantenerumab is required in DIAD mutation carriers compared to sAD to bring most participants below the amyloid threshold of positivity (20 centiloids) within 2 years and to fully remove amyloid plaques within 3-4 years. As greater amyloid removal is anticipated to increase the likelihood of subsequent improvement in cognitive and clinical response, this dose increase was considered necessary in the DIAD population. CCI

double-blind period of the DIAN-TU-001 trial as a higher dose significantly

reduced CSF total tau and phospho tau 181 (ptau181), and significantly slowed increases in CSF NFL.

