4 DRUG-SPECIFIC ANALYSIS PLAN

4.1 OLE Period

4.1.1 Biomarker Endpoint Statistical Analysis, Power and Sample Size Justification

The primary endpoint for the OLE period is PiB-PET composite SUVR.

The null hypothesis for the OLE period is that gantenerumab will not reverse the amyloid growth at the end of 3-year OLE compared to the OLE baseline for all participants who enroll into OLE: $H_0: \mu \geq 0$, where μ is the mean change from the OLE baseline to the end of 3-year OLE in PiB-PET SUVR. The alternative hypothesis is that gantenerumab reverses the amyloid growth: $H_a: \mu < 0$. The change from baseline will be analyzed using mixed model for repeated measures (MMRM) with baseline as a covariate in the model.

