4.1.2 Biomarker Endpoint Power Analysis

Based on DIAN-TU-001 data from the double-blind period, the mean (SD) change from the OLE baseline in PiB-PET composite SUVR to the end of the 3-year OLE period with dosing up to CCI [REDACTED] CCI [REDACTED] is projected to be at least -0.473 (0.540) for participants on gantenerumab from the beginning of the double-blind period, and participants starting gantenerumab in OLE (having been on either active solanezumab or placebo) together. The recruitment goal of OLE is to enroll 60 to 90 of the 144 mutation positive participants who participated in the placebo-control period. Assuming an annual dropout rate of 5%, at the end of 3-year OLE, there will be 51 to 77 participants and it will provide over 99% power to detect the projected mean change from baseline using a one-sided one-sample t-test with type I error 0.025.

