16.2.3.4. Primary Analysis of CSF pTau181

To evaluate whether gantenerumab will continue to reduce the CSF pTau181 from OLE baseline, MMRM (without controls) will be used to test if the change from the OLE baseline to the end of OLE in CSF pTau181 is significantly less than 0 for the OLE Gant mITT population. The MMRM will include the OLE baseline CSF pTau181 and visit (treated as categorical) as the fixed effects. An unstructured variance-covariance matrix will be used to model the within-subject errors among the repeated measures. If the unstructured covariance structure matrix results in a lack of convergence, the following covariance structures will be assumed in sequence: heterogeneous Toeplitz, heterogeneous autoregressive, heterogeneous compound symmetry, and compound symmetry. The corresponding p-value and the 95% confidence interval for the estimated least squares mean change at each visit will be presented. If the upper bound of the 95% CI at the year 3 OLE visit is less than 0, it is concluded gantenerumab significantly remove amyloid plaque at year 3.

[REDACTED] [REDACTED]

Author: [REDACTED]

Version Number:

7

Version Date:

07Dec2023

Template No.: CS_TP_BS016 Revision 6

Reference: CS_WI_BS005

Effective Date: 02Dec2019

Figures of model estimated mean over time by treatment arms or spaghetti plots of individual data over time/EYO by treatment arms will be presented as deemed necessary by Washington University team and may be included in CSR as needed. The plots will also be presented separately for baseline asymptomatic and symptomatic subjects at the OLE baseline.

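### The single-arm Year 3 PiB-PET interval leaves out the sampling variation in mean baseline, so it is too narrow for the population mean change whenever change correlates with baseline

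*SAP*

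**What the plan says.** Protocol Appendix 3, 4.1.1 states the hypothesis in terms of mu, which "is the mean change from the OLE baseline to the end of 3-year OLE in PiB-PET SUVR", with the null that mu is 0 or more. The same section says the change will be analysed by MMRM with baseline as a covariate.

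Appendix 3, 4.1.2 sizes the OLE "using a one-sided one-sample t-test with type I error 0.025". The mean (SD) change "is projected to be at least -0.473 (0.540") and 51 to 77 participants are expected at Year 3.

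SAP 16.1.3 fits the model to the OLE Gant mITT population without controls: "The MMRM will include the OLE baseline PiB-PET SUVR and visit (treated as categorical) as the fixed effects". Removal of plaque is concluded if the upper 95% limit for the Year 3 least squares mean change is below 0. The p-value that SAP 16.1.3 calls a one-sample t-test is computed from the least squares mean and its model standard error, so it is not the sizing test. The sandwich variance applies only if a structured covariance is needed, and it too conditions on baseline. Raw means and SDs are descriptive only.

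The same form recurs in SAP 16.2.3.4 ("The MMRM will include the OLE baseline CSF pTau181 and visit (treated as categorical) as the fixed effects"), in 16.2.3.5 and in the whole-study model of 16.1.4.3.

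**The concern.** In a randomised comparison, adjusting for baseline removes noise common to both arms, and the uncertainty in mean baseline largely cancels from the contrast. In one arm compared with 0 nothing cancels. The least squares mean is taken at the sample mean baseline, and its standard error counts only the residual scatter around the baseline regression. Had another sample with a different mean baseline been drawn, the mean change would also have differed; that component is missing.

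Some correlation between baseline and change is to be expected. Change contains baseline with a minus sign. The SAP allows for participants who start at normal amyloid levels and have little plaque to lose. The dose rationale in Appendix 3, 1.5.2.2 aims "to fully remove amyloid plaques within 3-4 years", and the nearer participants come to clearance, the closer change comes to minus the baseline excess.

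At stake are the coverage of the main estimate of amyloid removal and the stated one-sided 0.025 of the success rule.

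**Working it through.** **Inputs.** Mean change -0.473, SD of change 0.540, enrolment 60 to 90, 5% annual dropout, one-sided alpha 0.025 (Appendix 3, 4.1.2). Model and success rule from SAP 16.1.3. Rho is an assumption, shown as a range.

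**The plan's own figures reproduce.** 60 x 0.95^3 = 51.4 and 90 x 0.95^3 = 77.2, matching 51 to 77. By the noncentral t, power at -0.473 is above 99.99% for both. At -0.22 with n = 51 it is 81.4%, matching the stated figure of more than 80%. The sizing is sound.

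**Algebra (Year 3 only, complete data).** The least squares mean at mean baseline equals the raw mean change.

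- Sampling variance: SD^2/n.
- Variance the model reports: SD^2(1 - rho^2)/n.
- Missing part: rho^2 SD^2/n, which equals slope^2 x Var(baseline)/n.

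For n = 51: 0.540^2/51 = 0.005718, so SE 0.0756. At rho 0.5 the model reports 0.75 x 0.005718 = 0.004288, so SE 0.0655; the missing part is 0.25 x 0.005718 = 0.001429, and adding it restores 0.0756. The ratio of standard errors, sqrt(1 - rho^2), does not depend on n. Coverage is roughly P(|Z| < 1.96 sqrt(1 - rho^2)): 94% at 0.3, 91% at 0.5, 84% at 0.7.

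**The SAP's model.** It fits one baseline slope for all visits, which dampens the narrowing when the true slope grows over time. It was simulated with 60 enrolled, 5% annual dropout (about 51 at Year 3), unstructured covariance, REML and true mean change 0, with 2,500 to 3,000 trials per row. Further assumptions: SDs of change 0.30, 0.45 and 0.54 at Years 1 to 3; residual correlations 0.7 between adjacent visits and 0.55 between Years 1 and 3.

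| rho at Years 1/2/3 | Model SE | True SD of estimate | Coverage | One-sided error |
|---|---|---|---|---|
| 0/0/0 | 0.074 | 0.075 | 94.6% | 2.7% |
| 0.3/0.3/0.3 | 0.071 | 0.075 | 94.2% | 2.7% |
| 0.5/0.5/0.5 | 0.066 | 0.075 | 91.8% | 4.1% |
| 0.2/0.4/0.5 | 0.069 | 0.075 | 93.3% | 3.4% |
| 0.7/0.7/0.7 | 0.057 | 0.075 | 87.0% | 6.5% |
| 0.3/0.5/0.7 | 0.062 | 0.075 | 90.1% | 5.1% |

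In the same trials the paired one-sample interval on observed Year 3 changes covered 94.7-95.2%, with one-sided error 2.4-2.7%.

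**Which rho?** With r the correlation of baseline with the Year 3 value and s the ratio of the Year 3 SD to the baseline SD, the signed correlation is (rs - 1)/sqrt(1 + s^2 - 2rs). At s = 1 this gives -0.22, -0.32 and -0.50 for r = 0.9, 0.8 and 0.5. At r = 0.5 it gives -0.69 for s = 0.75 and -0.87 for s = 0.5. The documents give neither r nor s.

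**The primary decision.** 0.473/0.0756 = 6.3 standard errors at n = 51. The unconditional 95% interval at the design effect is -0.473 +/- 0.152, or -0.625 to -0.321. At n = 77 it is -0.473 +/- 0.123, or -0.596 to -0.350. All lie well below 0.

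**The case against.** **The cohort is closed.** Protocol 4.1.1 frames the null for everyone who enters the OLE, and "The recruitment goal of OLE is to enroll 60 to 90 of the 144 mutation positive participants". If inference is meant only for the baseline values actually enrolled, the planned interval is valid. That reading can be argued, but no such estimand is stated. The null concerns a mean mu, and the sizing test is unconditional, using the full SD of change.

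**The SAP follows the protocol.** A reader might infer that the SAP departed from the protocol. It did not: 4.1.1 prescribes the baseline covariate, and sizing with a simpler test is ordinary practice. This stands, so the correction has to reach protocol 4.1.1 as well.

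**The error rate could look far worse.** With a constant baseline slope, coverage is about 84% at rho 0.7 and 70% at 0.85, with one-sided error of 8% and 15%. The documents do not support headlining those figures. A 15-month titration means the Year 1 scan precedes the target dose, so a constant slope is unlikely. Correlations that high are argued from near-complete clearance, whereas type I error is evaluated at no mean change.

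**Nothing turns on it.** At the projected effect the decision is the same, SAP 7.4 makes no multiplicity adjustment, and the SAP's change history records early termination with no regulatory path. This stands as a limit on severity. It does not excuse a reported interval whose actual coverage falls short of its label.

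**Conclusion.** The concern holds in a limited form. For the population mean change, the Year 3 interval is too narrow whenever rho is not 0. The shortfall is nil at rho 0 and slight at 0.3. At 0.5 coverage is about 92-93% with one-sided error 3.5-4%; at 0.7 it is about 87-90% with error 5-6.5%. These figures rest on an assumed rho, the protocol's SD of 0.540, about 51 participants at Year 3, one common slope and the simulation settings listed above. Early termination may leave fewer Year 3 scans than planned; in the Year 3-only algebra the proportional narrowing does not depend on n.

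A reader might infer that the primary success conclusion is unsafe. It is not at the projected -0.473 and the planned numbers. A reader might also carry these percentages over to CSF pTau181, CSF Abeta1-42/40 and the whole-study model. They share the model form, but the documents give no effect, SD or correlation for them, so the effect there is unquantified. The harm shown is to the reported PiB-PET interval and to any result near 0.

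**What to change.** In SAP 16.1.3, put the OLE baseline value in the response vector as visit 0, with visit categorical, an unstructured covariance and no baseline covariate, and test the Year 3 minus baseline contrast. With complete data this reproduces the paired t-test used for sizing, and it keeps likelihood-based handling of missing follow-up scans. For consistency make the same change in 16.2.3.4, 16.2.3.5 and 16.1.4.3, using the baseline each of those analyses defines. Reconcile the baseline-covariate sentence in protocol Appendix 3, 4.1.1.

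If the pre-specified model must stay, report beside it an unconditional Year 3 interval: either a one-sample t on observed changes, or the least squares mean variance plus slope^2 x Var(baseline)/n. Base the success statement on that interval.

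The cost is a wider interval (half-width about 0.15 at n = 51) and a late change to a pre-specified model in a SAP version that postdates the interim. The change is in the conservative direction and needs no new data. Power stays above 99% at -0.473 and about 81% at -0.22 with n = 51. No gain should be claimed for participants with only a baseline scan, because the mITT definition in SAP 5.3 requires a post-baseline assessment.
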